Aim 2: We estimated DFS at 5 years among different treatment groups, using the Kaplan-Meier product-limit estimate of the survival curve. We also used the logrank statistic to assess for differences in DFS among the different treatment groups. Cox proportional hazards models were performed with the application of propensity scores. These Cox models estimated the hazard rate for each treatment type and evaluated differences in rates (rate ratios) between treatments, adjusting for confounding using propensity scores. We examined the proportional hazard assumption in each model and included time-varying covariates or incorporated a time*treatment interaction into the model when this assumption was not met.

Aim 3: We described the cumulative utilization for each category of health care (physician/specialty visits, hospitalizations, diagnostic tests/procedures, medications, prostate cancer treatment) within 4 years by treatment group. Specifically, we examined the proportion of patients in each treatment group who received each category of care (we created a

dichotomous variable indicating whether the patient received the care), and the count of services in each care category. We tested the differences in proportions between treatment groups using chi-square tests and differences in counts between treatment groups using t-tests. In multivariable analyses, we used logistic regression models and propensity score methods to estimate differences among groups in the proportions of patients receiving each category of care. Linear regression models incorporating propensity score methods were used to test differences among groups in the number of services received in each category. When counts of health care utilization were small (e.g., hospitalization) Poisson regression models were used.

Bias and Confounding: The use of the NCCCR RCA enabled all study participants to enroll prior to the initiation of treatment, thereby avoiding potential biases related to participation based on post-treatment outcomes. Furthermore, all baseline QOL data were collected before treatment, avoiding biases inherent to the recall of baseline information due to patient experiences during and after treatment. The following analytical methods were also employed to minimize and account for potential bias and confounding.

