1. **Propensity score methods:** We conducted propensity score analysis to assess for potential bias from measured confounders between treatment groups. Specifically, we used logistic regression to estimate the probability of receiving each treatment based on baseline characteristics and compute the propensity score from the model predicted probability of treatment for each participant. We examined the distribution of propensity scores across treatment groups and trimmed observations from the non-overlapping ends of the distribution as appropriate.⁵⁷ We then created inverse probability of treatment weights (IPTW) and stabilized these weights to reflect the sample size of each treatment group. IPTW was used in multivariable analyses to maximize the balance of confounding variables between the treatment groups. Propensity score matching using a “greedy algorithm”⁵⁸ and an alternative “optimal match”⁵⁹ algorithm was also considered as an approach to balance covariates across treatment groups.

2. **Assessment of sample balance:** To ensure balance of sample characteristics, we compared differences between treatment groups in the mean (for continuous variables) or distribution (for categorical variables) of each covariate by applying the generated propensity score weights. In addition, for propensity score-matched samples, we assessed the balance of study covariates using standardized differences across treatment groups. We added interaction terms to the propensity score model for the sample characteristics and risk factors that remained unbalanced after applying initial propensity score methods. When imbalances remained, we included the unbalanced variables in the multivariable outcome model(s) to ensure proper control of these confounding factors.
3. **Instrumental variables (IV):** We explored instrumental variable approaches to estimating the relationship between treatment and outcome while addressing potential unmeasured confounders. This method requires finding an appropriate “instrument” that is related to the exposure (treatment) but not directly related to the outcome, and meets all underlying IV assumptions.⁶⁰

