4. **Handling of missing data:** We followed the PCORI standards for handling and minimizing the impact of missing data. First, we carefully examined the pattern of missing data by individual items. We determined whether the missing data is informative, missing not at random (MNAR), missing completely at random (MCAR), or missing at random (MAR) by evaluating patient characteristics (e.g., age, race and ethnicity, treatment). We also compared those patients with missing data to patients with complete data. We then imputed missing data using a widely-employed multiple imputation approach.⁶¹ This method replaces the missing data with a set of m possible values by creating m imputed datasets through Monte Carlo technique. Each imputed dataset was analyzed using the same methods that are used for complete datasets. Results were pooled together to provide valid statistical inferences.⁶¹ These methods enabled us to use data from the entire study sample, including patients with differential follow-up, maximizing the study’s statistical power to detect differences among

treatment groups. Lastly, we conducted sensitivity analyses to examine the impact of the missing data on study results.^{62–65}

5. **Cluster analysis:** We examined for possible clustering within our study sample as data may have been clustered at several levels. For example, patients treated by the same physicians or facilities may have correlated outcomes, and patients living in the same area may share characteristics related to treatment outcomes. To account for clustering in our analysis of DFS (Aim 2), we conducted proportional hazard model using a robust sandwich estimate⁶⁶ and likelihood-based random effect (frailty) model.⁶⁷ For outcomes analyzed by linear and logistic regression models, we used GEE modeling approaches to obtain appropriate standard errors, and/or applied multilevel modeling to explicitly model the clustered data structures and allow for random intercepts of the higher level data structure.

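### Aim 2 describes no adjusted 5-year DFS: the Kaplan-Meier figures and log-rank test carry no stated weighting, and propensity scores reach only the Cox rates and rate ratios

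*Combined protocol and SAP*

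**What the plan says.** Under Outcome Measures, Primary Outcome 2 is a direct comparison of disease-free survival among treatment options over 5 years. The design is an observational cohort with a non-probability sample.

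In Analytical and Statistical Approaches, Aim 2 has two layers:

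- **Curves and test.** "We estimated DFS at 5 years among different treatment groups, using the Kaplan-Meier product-limit estimate of the survival curve". Then: "We also used the logrank statistic to assess for differences in DFS among the different treatment groups". Neither sentence mentions weights, matching or stratification.
- **Cox models.** Propensity scores enter here. The stated outputs are rates: "These Cox models estimated the hazard rate for each treatment type and evaluated differences in rates (rate ratios) between treatments".

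Bias and Confounding, item 1, gives the scope of the weights: "IPTW was used in multivariable analyses to maximize the balance of confounding variables between the treatment groups". Item 2 handles residual imbalance, also inside regression models: "When imbalances remained, we included the unbalanced variables in the multivariable outcome model(s) to ensure proper control of these confounding factors". Item 4 repeats the analysis in each imputed dataset, and item 5 deals with clustering for DFS: "To account for clustering in our analysis of DFS (Aim 2), we conducted proportional hazard model using a robust sandwich estimate", with a frailty model beside it. No section describes a weighted survival curve or a 5-year DFS probability standardised from the Cox model.

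**The concern.** Men were not allocated to treatment at random, and the section on treatment outcome heterogeneity itself lists race and ethnicity, age and disease severity as confounders. A group with more high-risk men will show lower crude 5-year DFS even if its treatment works equally well, and a log-rank test on the same data will tend to confirm the difference.

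The adjusted rate ratio does not replace the missing figure. It is a relative measure, whereas the outcome is framed at 5 years. If proportional hazards fails, Aim 2 allows a time-by-treatment term, and one ratio then no longer summarises the contrast. The Detailed Description says the results should help patients choose between treatments. Percentages disease-free at 5 years are easily read for that purpose, and they are the figures left without a stated adjustment.

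**Working it through.** The documents give no DFS rate, event count, group size, alpha or power for Aim 2, so there is no planned figure to reproduce. The check has a textual part and an illustrative part.

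**1. Text.**

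| Aim 2 output | Stated method | Stated adjustment |
|---|---|---|
| 5-year DFS by group | Kaplan-Meier | none |
| Test of difference between curves | log-rank | none |
| Hazard rates, rate ratios | Cox | propensity scores |

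Kaplan-Meier and log-rank are not multivariable analyses, so the scope given for IPTW in item 1 does not on its face include them. Matching is said only to have been considered, and is not tied to the curves.

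**2. Arithmetic, assumed inputs, no treatment effect within risk strata.** With two risk strata,

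crude gap = (difference in high-risk share) × (difference in 5-year DFS between strata).

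- Differences of 5 to 30 points in share and 10 to 33 points in DFS give 0.05 × 0.10 = 0.5 point up to 0.30 × 0.33 = 9.9 points.
- Low-risk DFS 95%, high-risk 85%, shares 20% and 30%: 0.20 × 0.85 + 0.80 × 0.95 = 93.0% against 0.30 × 0.85 + 0.70 × 0.95 = 92.0%, a gap of 1.0 point.
- Low-risk DFS 95%, high-risk 75%, shares 10% and 50%: 0.10 × 0.75 + 0.90 × 0.95 = 93.0% against 0.50 × 0.75 + 0.50 × 0.95 = 85.0%, a gap of 8.0 points. Standardised to the mean share of 30%, both groups are 0.30 × 0.75 + 0.70 × 0.95 = 89.0%, a gap of 0.

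At an assumed 300 men per group and two-sided 5%, an unadjusted 5-year comparison would be significant with probability about 0.07 in the first of these examples and 0.88 in the second.

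**3. Simulation, every input assumed except N = 1656.** There were 2000 cohorts per setting, six measured covariates driving treatment choice, overall 5-year DFS 83.5%, censoring only at 5 years and no treatment effect. There were three equal groups, or four groups of 30/30/30/10%. Selection strength was tuned to give the largest crude gap in the first column. That column is therefore a chosen setting; the other columns follow from it.

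| Largest crude gap (set), points | Smallest pairwise gap, points | Men in top fifth of risk, across three groups | Log-rank rejects, three groups | Log-rank rejects, four groups |
|---|---|---|---|---|
| 0 | – | 20–20% | 5.3% | 4.5% |
| 0.5 | 0.1–0.3 | 19.4–20.6% | 6.1% | 5.7% |
| 1 | 0.2–0.5 | 18.8–21.2% | 6.5% | 5.8% |
| 3 | 0.7–1.5 | 16.4–23.8% | 20.6% | 15.3% |
| 6 | 1.4–2.7 | 12.9–27.7% | 67.3% | 48.5% |
| 10 | 2.4–4.4 | 8.4–33.3% | 98.9% | 92.0% |

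With stabilised IPTW on the curves, mean gaps are within 0.11 point (0.43 after trimming). The robust Wald test from the weighted Cox model rejects in 2.2–4.8% of cohorts across all settings.

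**4. Check of the remedy, three groups.** This adds 30 physicians per group (log-frailty SD 0.4), 15% loss to follow-up, about 15% of values missing at random in the strongest covariate, 5 imputations, and 60 cluster-bootstrap resamples per imputation with the propensity score refitted in each.

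| Setting | Weighted gaps within | 95% CI coverage | Coverage ignoring clusters | Wald rejects | Wald ignoring clusters |
|---|---|---|---|---|---|
| 3 points (1343 cohorts) | 0.06 point | 92.9–93.9% | 89.9–90.8% | 5.8% | 10.2% |
| 10 points (1344 cohorts) | 0.19 point | 94.0–94.8% | 90.2–92.5% | 5.3% | 8.5% |

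Interval half-widths were about 5.2–6.4 points. The lowest coverage, 92.9%, has Monte Carlo error √(0.929 × 0.071 / 1343) = 0.70 point, so it lies 2.1/0.70 = 3.0 standard errors below 95%: slight under-coverage.

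**The case against.** The strongest reply is that the comparison is already adjusted. All three aims follow the same layout, simple summaries and tests first and propensity-score models second, so the curves and log-rank can be read as a descriptive first layer. This stands in part: crude curves are legitimate description, and the Cox comparison is not faulted here. But the plan does not label them descriptive, and they are its only stated 5-year figures.

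Second, Aim 2 says the Cox models give a hazard rate for each treatment, from which 5-year survival is a short step. The step is short but is not described. It needs a baseline hazard, and averaging over covariates whenever unbalanced variables have been added to the model.

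Third, the text is silent and does not say the curves were unweighted; weighted or matched curves may have been produced. That is correct, and it is why the first request is to state which was done.

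Fourth, the simulated gaps are settings and not evidence of size, and IPTW succeeds there because every confounder is measured. Both points stand. The calculation shows what crude figures can do and that the remedy works under measured confounding; it does not show how large the error is in this cohort. The remedy check also covers only three groups, although Primary Outcome 1 names four, and it did not test Cox-standardised survival.

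**Conclusion.** The concern holds, within narrow limits. As described, the absolute 5-year DFS by treatment and the log-rank p-value for a primary outcome are unadjusted in a non-randomised cohort, and no adjusted 5-year figure is described. The propensity-score Cox ratios are unaffected.

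The size is unknown. On assumed inputs it runs from negligible (0.5 point, log-rank rejecting about 6% against a nominal 5%) to large (about 10 points, 92–99%). Which end applies depends on the risk mix by treatment, which the documents do not report. This is an inexpensive improvement to the analysis and does not invalidate Aim 2.

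**What to change.** 1. State whether the Kaplan-Meier curves and log-rank test were weighted. If not, label both descriptive.
2. Add an adjusted 5-year DFS per group, with pairwise differences and 95% confidence intervals, beside the rate ratios. Either apply the existing stabilised IPTW to the Kaplan-Meier curves, which needs no proportional-hazards assumption, or standardise survival from the weighted Cox model, which can also carry covariates left unbalanced after weighting.
3. For the intervals, bootstrap by physician or facility within each imputed dataset, refit the propensity score in every resample, and pool with Rubin's rules. This follows the plan's own statements that "patients treated by the same physicians or facilities may have correlated outcomes" and "Each imputed dataset was analyzed using the same methods that are used for complete datasets".
4. Use the cluster-robust Wald test from the weighted Cox model, pooled over imputations, as the between-group test, jointly with any time-by-treatment term.

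**Cost.** The document is dated 1 Jan 2019 and written in the past tense, so this is an added analysis and a reporting statement with no new data. Weights, imputed datasets and clustering methods are already described. The sandwich estimate in item 5 covers the Cox model only, so the 5-year intervals need new programming. Precision may fall where selection is strong: the SD of the 5-year difference was up to 1.37 times crude in the 10-point setting, against 0.89–1.09 times with none to moderate selection. Weighting removes measured confounding only, and the report should say so.

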NC ProCESS is a population-based cohort designed specifically to address well-described knowledge gaps. It was designed in close collaboration with the unique AHRQ consortium stakeholder group, which included representatives from patients, clinicians and policymakers. Stakeholders helped define study design to emphasize "real-world" patients and select patient-centered and relevant outcomes, and have been involved throughout assembly of this patient cohort. The diverse cohort is well-represented by "hard to reach" patients; enrollment before treatment avoids biases with participation and recall. As clinical trials are not feasible to address the central questions in prostate cancer CER, this prospective study will yield the

highest level of evidence to inform patients and other stakeholders. With an assembled cohort, this study is necessary to examine comparative outcomes.

Study Design:

Study Type:	Observational
Actual Enrollment:	1656 participants
Observational Model:	Cohort
Time Perspective:	Prospective
Study Start Date:	January 2011
Estimated Primary Completion Date:	December 2018
Estimated Study Completion Date:	December 2018

Outcome Measures:

Primary Outcome Measure:

1. Patient Reported Outcomes [Time Frame: 4 years]
Directly compare patient-reported prostate-cancer specific and global quality of life (QOL), anxiety regarding prostate cancer and decisional regret in a cohort of men with localized prostate cancer managed by active surveillance, radical prostatectomy, radiation therapy, and brachytherapy.
2. Disease-Free Survival [Time Frame: 5 years]
Directly compare the disease-free survival among different treatment options for prostate cancer.
3. Directly compare health care utilization among different treatment options for prostate cancer from review of medical records [Time Frame: 4 years]
For each treatment group (radiation therapy, prostatectomy, active surveillance), we will describe the cumulative utilization for each category of health care. These categories are physician/specialty visits, hospitalizations, diagnostic tests/procedures, medications, and prostate cancer treatments (for the initial cancer and for recurrence).
Measurements will be attained by review of medical records.

Eligibility Criteria:

Ages Eligible for Study:	35 Years to 80 Years
Sexes Eligible for Study:	Male

Accepts Healthy Volunteers: No
Sampling Method: Non-Probability Sample

Study Population

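### Aim 2's disease-free survival analyses are weighted for treatment received but not for loss to follow-up, so they assume that loss is unrelated to prognosis within each treatment group

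*Combined protocol and SAP*

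**What the plan says.** DFS at 5 years is listed as a primary outcome (Outcome Measures, item 2). Under Analytical and Statistical Approaches, Aim 2, the plan has three steps:

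- Group curves: "We estimated DFS at 5 years among different treatment groups, using the Kaplan-Meier product-limit estimate of the survival curve".
- A logrank comparison of the treatment groups.
- Adjusted comparison: "Cox proportional hazards models were performed with the application of propensity scores".

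Bias and Confounding, item 1, says what the scores are: "we used logistic regression to estimate the probability of receiving each treatment based on baseline characteristics". The weights follow: "We then created inverse probability of treatment weights (IPTW) and stabilized these weights to reflect the sample size of each treatment group". Their purpose is baseline balance: "IPTW was used in multivariable analyses to maximize the balance of confounding variables between the treatment groups". Under item 2, a covariate enters the outcome model only if it is still unbalanced between treatment groups after the propensity methods have been applied.

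Item 4 (missing data) starts from missingness by item, applies multiple imputation, and says this lets the whole sample be used, "including patients with differential follow-up". It ends with unspecified sensitivity analyses for missing data. Item 5 gives DFS a robust sandwich variance and a frailty model, both for clustering.

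No section gives a censoring rule for DFS, a model for time to loss, or censoring weights.

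**The concern.** Treatment weights balance measured factors when follow-up starts. They do not keep the groups balanced among the men still under observation in later years. A weighted Cox model with treatment as its only term needs censoring to be independent of prognosis given treatment alone. Kaplan-Meier and logrank need the same condition within each group. A correctly specified Cox model that included the risk factors would tolerate loss explained by them. The weighted model does not, unless those factors happen to be in it because of leftover treatment imbalance. That trigger has nothing to do with whether a factor predicts loss.

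If older men or men with more severe disease drop out sooner, the estimated 5-year DFS is too high. If they do so more strongly in one treatment group, that group looks better than it is. This could happen through factors the study has already measured and put in its propensity model.

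**Working it through.** **No figure to reproduce.** The documents give no DFS event count, loss rate or power calculation. The check is therefore of the mechanism, on assumed inputs.

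**Assumptions.** Two equal-sized groups, perfectly balanced at baseline by the treatment weights. In each, 35% of men are at higher risk with 5-year DFS of 65%; the rest have 92%. There is no treatment effect. Annual loss is 2% for everyone in the comparison group and for lower-risk men in the other group. Annual loss of higher-risk men in that other group is varied.

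**True DFS.** 0.35 × 0.65 + 0.65 × 0.92 = 0.8255, or 82.6%, in both groups.

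**Hazards per year.** Higher risk: −ln(0.65)/5 = 0.0862. Lower risk: −ln(0.92)/5 = 0.0167.

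**Men at risk at time t**, with annual loss c in a stratum of share p and event hazard h: Y(t) = p × exp(−ht) × (1 − c)^t.

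**Illustration at 5 years, with 12% loss of higher-risk men.**

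- Comparison group: the common loss factor cancels, so the higher-risk share of those at risk is 0.2275/(0.2275 + 0.5980) = 27.6%. The pooled hazard is 0.276 × 0.0862 + 0.724 × 0.0167 = 0.0358.
- Other group: higher-risk 0.2275 × 0.88^5 = 0.1201; lower-risk 0.5980 × 0.98^5 = 0.5405; share 0.1201/0.6606 = 18.2%. The pooled hazard is 0.182 × 0.0862 + 0.818 × 0.0167 = 0.0293.

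Groups that were identical at entry now show different hazards with no treatment effect.

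**Over the full 5 years.** The Kaplan-Meier limit is exp(−∫ pooled hazard dt). The Cox hazard ratio θ solves the large-sample score equation: events in the affected group = ∫ (all events at t) × θY1/(θY1 + Y0), where Y1 and Y0 are the numbers at risk. The proportion lost sums, over strata, p × r/(h + r) × [1 − exp(−5(h + r))] with r = −ln(1 − c).

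| Annual loss, higher-risk men, one group only | Lost by 5 years (comparison 8.7%) | Kaplan-Meier DFS (true 82.6%) | Cox HR (true 1.00) |
|---|---|---|---|
| 2% | 8.7% | 82.6% | 1.00 |
| 4% | 11.3% | 82.9% | 0.98 |
| 6% | 13.6% | 83.2% | 0.96 |
| 8% | 15.8% | 83.5% | 0.95 |
| 12% | 19.7% | 84.1% | 0.91 |
| 20% | 25.9% | 85.2% | 0.85 |

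**Limiting cases.** With 12% loss of higher-risk men in both groups, the hazard ratio is 1.00 but DFS reads 84.1% in each. With 8% in one group and 5% in the other, the hazard ratio is 0.97. If loss is unrelated to risk, there is no bias.

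**Second check, by simulation with weights.** Assumptions: one measured binary factor (40% prevalence), propensity 0.6 with it and 0.4 without, baseline event hazard 0.03 per year, baseline loss 0.05 per year, true hazard ratio 1.00. Where the factor tripled risk and raised loss 5-fold in one group only (about 20% against 40% lost), the treatment-weighted Cox hazard ratio was 0.90. Multiplying by censoring weights estimated from treatment and the same factor returned it to 0.999. Across the five one-sided-loss settings tried at the null, treatment weights alone gave 0.84 to 0.97 and the combined weights 0.995 to 1.003. When the factor tripled loss equally in both groups, the hazard ratio was essentially unbiased and DFS was too high by about 0.5 to 2 points.

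**The case against.** Four points on the other side deserve weight.

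- **Differential follow-up.** A reader might infer that the plan admits follow-up differs by treatment or by risk. It does not. The phrase sits in a general missing-data paragraph covering all aims and says nothing about treatment group, prognosis or DFS. This stands.
- **Hazard ratio.** A reader might infer that any risk-related loss biases the hazard ratio. It does not: the loss-risk relation must differ between treatment groups, and the documents give no evidence that it does. Moderate differences produce small shifts (0.98 and 0.96 in the table). This stands too.
- **The Cox model's covariates.** They are not fully specified. Unbalanced variables may be added, time-varying terms are allowed if proportional hazards fail, and matching was considered. So a treatment-only model is the default reading, not a certainty. Covariates brought in for imbalance would weaken the assumption to independence given those covariates, but they are not chosen because they predict loss.
- **Missing-data section.** It compares men with and without missing data, considers data missing not at random, and promises sensitivity analyses. This might be read as covering censoring. But a censored DFS time is not a missing item; the planned survival methods accept it as non-informative, and the text never says that event times were imputed or censoring examined. Nor does silence show that censoring was ignored. It is a gap in what is specified.

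**Conclusion.** The point holds in a limited form. As written, the DFS comparison relies on loss being unrelated to prognosis within each treatment group, except as relaxed by any still-unbalanced covariates in the Cox model, and the plan neither states nor tests this. Absolute 5-year DFS is exposed whenever loss depends on risk; the hazard ratio is exposed only if that dependence differs by treatment group.

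The sizes calculated here are illustrations. They depend on the assumed risk mix and loss rates, on higher-risk men leaving sooner, and on a comparison group with no link between loss and risk; if lower-risk men left sooner, the bias would run the other way. The documents support no claim that the study's hazard ratios are in fact biased, or in which direction. The case for acting is that this is a primary outcome, that the assumption can be examined with covariates already collected, and that the change is cheap.

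**What to change.** In Aim 2:

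1. State the DFS censoring rules, and whether the imputation and sensitivity analyses in Bias and Confounding, item 4, extend to DFS times.
2. Report loss to DFS follow-up by treatment group and baseline risk.
3. Estimate stabilized inverse-probability-of-censoring weights separately by treatment group, from a model for time to loss using the propensity-model covariates. Multiply them by the treatment weights.
4. Report the resulting weighted DFS curves and Cox model, with robust sandwich variance, alongside the treatment-weight-only result. At minimum this should be a sensitivity analysis specified before it is run, with the statement that a difference between the two qualifies the DFS conclusion. Which result is presented first need not be dictated.

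The cost is one additional model and some SAP wording, with no new data. The weights become somewhat more variable and the intervals slightly wider. Loss driven by unmeasured factors is not corrected, and the report should say so.

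### The plan names no cluster-robust variance and no overdispersion check for the Poisson models of small utilization counts in Aim 3, so their standard errors can be wrong

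*Combined protocol and SAP*

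**What the plan says.** The combined protocol and SAP lists health care utilization over 4 years as its third primary outcome: "For each treatment group (radiation therapy, prostatectomy, active surveillance), we will describe the cumulative utilization for each category of health care".

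Under Analytical and Statistical Approaches, Aim 3, the number of services in each category is modelled in two ways. The general rule is: "Linear regression models incorporating propensity score methods were used to test differences among groups in the number of services received in each category". The exception is: "When counts of health care utilization were small (e.g., hospitalization) Poisson regression models were used". That sentence is the only mention of Poisson in the documents. It names no standard error, dispersion or cluster method. Unlike the linear and logistic sentences beside it, it does not mention propensity scores. Weighting of the Poisson models is apparent only from the general statement under Bias and Confounding, item 1: "IPTW was used in multivariable analyses to maximize the balance of confounding variables between the treatment groups".

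Bias and Confounding, item 5 (Cluster analysis) gives the reason for adjusting standard errors: "patients treated by the same physicians or facilities may have correlated outcomes". It then assigns methods by model type:

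- Survival: "To account for clustering in our analysis of DFS (Aim 2), we conducted proportional hazard model using a robust sandwich estimate", together with a frailty model.
- Linear and logistic: "For outcomes analyzed by linear and logistic regression models, we used GEE modeling approaches to obtain appropriate standard errors", and/or multilevel models with random intercepts.

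Poisson is not assigned a method.

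**The concern.** Of the regression families in the plan, Poisson is the only one without a stated remedy for correlated outcomes. It is also the one whose default variance is most restrictive. Linear regression estimates its residual variance from the data, whereas ordinary Poisson regression fixes the variance at the mean. Extra between-patient variation in a four-year hospitalization count is therefore not absorbed, and correlation within a physician's or facility's patients is ignored.

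At stake are the confidence intervals and p-values for treatment differences in small counts. If default errors were used and counts are overdispersed, or clustered by treatment, those differences would look more precise than they are. Only the small-count models in Aim 3 are affected. Hospitalization is the one example given, and this is part of one of three primary outcomes.

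**Working it through.** The plan gives no count rate, dispersion, intraclass correlation (ICC), cluster number or test level, so it has no figure to reproduce. Only the enrollment of 1656 comes from the documents. Every other input below is an assumption.

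**1. Overdispersion alone.** Let D be variance/mean. The model-based standard error is too small by a factor √D, so a nominal 5% two-sided Wald test has actual type I error 2 × (1 − Φ(1.96/√D)). A correct log-scale interval is √D times as wide.

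| D | 1.96/√D | Type I error | Width ratio √D |
|---|---|---|---|
| 1 | 1.960 | 5.0% | 1.00 |
| 1.25 | 1.753 | 8.0% | 1.12 |
| 1.5 | 1.600 | 11.0% | 1.22 |
| 2 | 1.386 | 16.6% | 1.41 |

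Simulated negative binomial counts (20,000 runs, two groups of 1656/3 = 552, mean 0.3 to 1.0) agreed: about 5% at D = 1, 11% at 1.5 and 16–17% at 2. A sandwich variance gave 4.7% to 5.5% for D from 1 to 3.

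**2. How much heterogeneity this needs.** In a gamma-Poisson model, D = 1 + mean × v, where v is the variance of the patient-level rate multiplier. D = 2 needs v = 1/0.5 = 2 at mean 0.5, 1/0.2 = 5 at mean 0.2 and 1/0.1 = 10 at mean 0.1. The smaller the count, the harder it is to reach the lower rows of the table.

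**3. Clustering alone.** Take m men per cluster, of whom a share p receives the cluster's main treatment, with the two treatments balanced overall and counts Poisson within a cluster. The true variance of the treatment contrast, relative to the Poisson value, is then D = 1 + m(2p − 1)² × ICC/(1 − ICC). For example, m = 12, p = 1 and ICC 0.02 give 1 + 12 × 0.02/0.98 = 1.245. Putting D into the step 1 formula gives, for ICC 0.01, 0.02 and 0.05:

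| Clusters (1104 men) | p = 0.5 | p = 0.75 | p = 1 |
|---|---|---|---|
| 92 physicians × 12 | 5.0%, 5.0%, 5.0% | 5.4%, 5.7%, 6.9% | 6.4%, 7.9%, 12.5% |
| 24 facilities × 46 | 5.0%, 5.0%, 5.0% | 6.4%, 7.8%, 12.2% | 10.5%, 15.9%, 28.9% |

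At p = 0.5 the term (2p − 1)² is zero and clustering drops out. The right-hand column requires every physician or facility to give a single treatment. In simulation, a cluster-robust variance gave 4.7–6.1% with 92 clusters and 6.0–7.1% with 24, so it remains slightly liberal when clusters are few.

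**4. The opposite direction.** The documents do not say whether the index surgical stay counts as a hospitalization. Suppose it does: a surgical patient's count is 1 + X and a comparator's is X, where X has mean 0.5 and variance 0.5D. Per patient and on the log scale, the model-based variance is 1/1.5 + 1/0.5 = 2.667. The true variance is 0.5D/1.5² + 0.5D/0.5² = 2.222D. The ratio is 0.833D. At D = 1, 1.25, 1.5 and 2, the nominal 95% interval misses the true ratio 3.2%, 5.5%, 8.0% and 12.9% of the time. At D = 1 the default standard error is too large.

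**The case against.** The strongest reply is that this is an omission from one sentence, not a demonstrated error. The Cluster analysis item opens by examining clustering in the whole study sample and is not confined to particular aims. GEE and multilevel models extend directly to Poisson, so the analysts may well have used them and left Poisson out when listing model types. This stands as far as it goes: a reader might infer that Aim 3 was analysed with default standard errors or that its precision is overstated, and the documents support neither inference. But the GEE sentence is worded for linear and logistic models, and even a generous reading does not supply an overdispersion check.

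Four further points limit the concern:

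- **Inputs.** The dispersion ratios, ICCs, cluster numbers and treatment shares are all assumed. A reader might take the highest clustering figures as expected values. They need single-treatment facilities, and small counts make large dispersion ratios harder to reach.
- **Direction.** The error need not be anticonservative, as step 4 shows.
- **Partial safeguards.** Aim 3 also compares counts by t-test, whose variance is empirical, and any use by logistic regression, which the Cluster analysis item covers. The t-tests are unadjusted and ignore clustering, so the protection is incomplete.
- **Weighting.** A reader might infer that Poisson alone lacks a variance suited to the weights. No model in the plan is given a variance tied to the weights, so this is not a Poisson-specific gap and no weighted error rates are counted here.

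**Conclusion.** The concern holds in a limited form. Poisson regression fitted as named, with nothing added, takes variance equal to the mean, independence and no effect of weighting on the variance. The plan's own statement about correlated outcomes gives reason to doubt the independence assumption, and its remedies stop short of these models.

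The inflation is nil when variance equals the mean and treatments are mixed within clusters. It is moderate at the assumed dispersion ratios of 1.25 to 1.5, and larger only under stronger assumptions. The true size is unknown, because neither the variance actually used nor any dispersion or cluster figure is given. With one narrow set of models affected, severity is low to moderate. This is a cheap improvement, and nothing here shows that the utilization results are invalid.

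**What to change.** Extend the linear/logistic sentence in Bias and Confounding, item 5 to the Poisson models: a robust sandwich or GEE variance clustered on physician or facility, with a small-sample correction if clusters are few. State which variance was in fact used, say whether the index surgical stay is counted as a hospitalization, and report the Pearson dispersion. A negative binomial sensitivity analysis is optional.

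The cost is one or two sentences, plus a re-run of the Poisson models only if model-based errors were used. With an independence working model the point estimates do not change. Intervals may widen, by about 12% to 41% on the log scale at assumed variance/mean 1.25 to 2, and could narrow if a group is underdispersed. The t-tests, linear models and logistic models can stay as they are.
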